
10.
	
Clinic Staff conducts introductions, reviews process, and checks for Patient readiness.
 
 
• Has Clinic Staff introduced themselves? 
 
✓ Name and Roles
 
 
 
• Has Clinic Staff reviewed the procedure process for the day? 
 
✓ Go over what the Patient can expect during the days procedure
 
 
 
• Has Clinic Staff ensured Patient readiness? 
 
✓ Answer any questions the Patient may have; and
 
✓ Check to see if Patient needs to use the restroom prior to procedure.
 
 
 
 
➤ If NO > Step must be completed prior to proceeding.
 
➤ If YES > Proceed to Step 11 of this SOP

11.
	
Clinic Staff obtains vitals.
 
 
• Has Clinic Staff obtained the following vitals? 
 
✓ Blood Pressure;
 
✓ Pulse;
 
✓ Heart Rate;
 
✓ Respiratory Levels;
 
✓ SaO Levels;
 
✓ EKG (If required, per Practitioner's judgement); and
 
✓ PFT (May be obtained within the 3 days of scheduled treatment)
 
 
 
 
➤ If NO > Obtaining Patient vitals is required prior to proceeding.
 
➤ If YES > Proceed to Step 12 of this SOP

12.
	
Clinic Staff completed the subjective/chief complaint.
 
 
• Has Clinic Staff completed the Subjective/Chief Complaint? 
 
✓ Patient Complaint/Primary Reason for Visit (i.e.: Patient here for shortness of breath, second day of procedure, COPD Treatment, etc.)
 
 
 
 
➤ If NO > Step must be completed prior to proceeding.
 
➤ If YES > Proceed to Step 13 of this SOP

10Mar2016 - version 2.0

LI-001

13.
	
Is today the first treatment day for the Patient?
 
➤ If NO > Proceed to Step 16 of this SOP
 
➤ If YES > Proceed to Step 14 of this SOP

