21.	
Clinic Staff conducts on-going oversight of Patient during administration.
 
 
• Has Clinic Staff confirmed the patency and flow are correct?
 
 
➤ If NO > Step must be completed prior to proceeding.
 
➤ If YES > Proceed to Step 22 of this SOP

22.	
Clinic Staff starts nebulizer treatment.
 
 
• Has Clinic Staff completed the following? 
 
✓ Place glutathione and saline into nebulizer medicine cup and provide Patient with instructions to begin nebulizing treatment; and
 
 
 
 
➤ If NO > Step must be completed prior to proceeding.
 
➤ If YES > Proceed to Step 23 of this SOP

10Mar2016 - version 2.0

LI-001

23.	
Clinic Staff discontinues IV line and nebulizer; and provide post care instructions.
 
 
• Has the Clinic Staff completed the following? 
 
✓ Turn off nebulizer when treatment completed;
 
✓ When final product has emptied IV bag, use normal saline flush to flush entire contents of IV line;
 
✓ Remove IV catheter;
 
✓ Place 2x2 gauze pad over site, affix coban bandage;
 
✓ Instruct Patient to remove gauze and coban after 20 to 30 minutes; and
 
✓ Dispose of supplies in designated biohazard containers.
 
 
 
 
➤ If NO > Step must be completed prior to proceeding.
 
➤ If YES > Proceed to Step 24 of this SOP

-----	---

24.	
Has Clinic Staff provides Patient with discharge folder and post-care instructions and answered any Patient questions or concerns?
 
 
• Has Clinic Staff advised the Patient of the below post-care instructions and ensured that they understand said instructions; answering any questions or concerns? 
 
✓ Briefly review and explain the discharge folder contents to Patient;
 
✓ Review LI follow-up procedures; and
 
✓ Review Patient Journals for quality of life outcome data.
 
 
 
 
➤ If NO > Step must be completed prior to proceeding.  ➤ If YES > Proceed to Step 25 of this SOP

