8.	
Has Clinic Staff conducted introductions, review process, and checks for readiness?
 
 
• Clinic Staff introduces themselves; 
 
✓ Name and Roles
 
 
 
• Reviews the procedure process for the day; and 
 
✓ Go over what the Patient can expect during the days procedure
 
 
 
• Ensure Patient readiness 
 
✓ Answer any questions the Patient may have; and
 
✓ Check to see if Patient needs to use the restroom prior to procedure.
 
 
 
 
➤ If NO > Preparation is required prior to proceeding.
 
➤ If YES > Proceed to Step 9 of this SOP

9.	
Clinic Staff obtains vitals.
 
 
• Has the Clinic Staff obtained Patient Vitals? 
 
✓ Blood Pressure;
 
✓ Pulse;
 
✓ Heart Rate;
 
✓ Respiratory Levels;
 
✓ SaO Levels;
 
✓ EKG (Required to be obtained prior to Bone Marrow Procedure); and
 
✓ PFT (May be obtained within the 3 days of scheduled treatment)
 
 
 
 
➤ If NO > Obtaining Patient vitals is required prior to proceeding.
 
➤ If YES > Proceed to Step 10 of this SOP

10.	
Clinic Staff completed the subjective/chief complaint.
 
 
• Has Clinic Staff completed the Subjective/Chief Complaint? 
 
✓ Patient Complaint/Primary Reason for Visit (i.e.: Patient here for shortness of breath, second day of procedure, COPD Treatment, etc.)
 
 
 
 
➤ If NO > Step must be completed prior to proceeding.
 
➤ If YES > Proceed to Step 11 of this SOP

11.	
Is today the first treatment day for the Patient?
 
➤ If NO > Proceed to Step 13 of this SOP
 
➤ If YES > Proceed to Step 12 of this SOP

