42.	
Clinic Staff gives Patient post-op instructions.
 
 
• Has Clinic Staff advised the Patient of the below post-op care instructions and ensured that they understand said instructions; answering any questions or concerns? 
 
✓ Do not shower until after next-day clinic visit; only sponge bath and avoid water to bandaged area;
 
✓ Avoid excessive lifting and bending for the next seven days; and
 
✓ To use ice for 15 minute sessions at least twice within the day.
 
 
 
 
➤ If NO > Step must be completed prior to proceeding.
 
➤ If YES > Proceed to Step 43 of this SOP

------------	---

10Mar2016 - version 2.0

LI-001

43.	
Has Clinic Staff updated EMR as required?
 
 
• Capture procedure as required in the EMR: 
 
✓ Vitals
 
✓ Testing Conducted
 
✓ Medications Administered
 
✓ Lot Numbers and expirations (As Applicable);
 
✓ Dosage(s)
 
✓ Site(s) of Procedure and/or Administrations (Left vs Right, and location)
 
✓ Route (PO, SubQ, IM, IV, Etc.); and
 
✓ Any additional notation or documentation required (e.g.: Checklists and/or Flowsheets).
 
 
 
 
➤ If NO > Step must be completed to complete SOP.
 
➤ If YES > SOP Complete

Notes:	
Related Documents: P&P CL-005	

10Mar2016 - version 2.0

LI-001

Lung Institute Clinical Procedure
	
Standard Operating Procedure (SOP) Discharge Treatment Day Procedure

Issue Date: 11/20/2015  Last Revision Date: 3/7/2016  Date: Clinical Department  Owner: [name], ARNP – Lung Institute Operations  Document Author: Medical Director  Approved By:
	

Purpose:
	To outline the clinical Discharge Treatment Procedure, to ensure Patient and employee safety and minimize risk of exposure or incident.

Primary User:  Other department(s) Affected:
	LI-Clinical Department RMS-Records Department

**Systems Used:** EMR; ZOHO

These instructions encompass the process for the preparation and completion of the Discharge Procedure. Steps must be completed in sequential order unless instructed to skip steps in procedure work flow.

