6.	
Clinic Staff must properly prepare mayo stand under a clean technique for Patient procedure.
 
 
• Has the Clinic Staff prepared the mayo stand by covering with underpad and ensuring all the following is made available? 
 
✓ 30ml Syringe with ACD-A
 
✓ 20g or 22g IV Catheter
 
✓ Alcohol Prep Pad(s)
 
✓ 2x2 Gauze
 
✓ IV Starter Kit
 
 
 
• Has the Clinic Staff hung the IV bag in the exam room on the IV pole? 
 
✓ Previously spiked 100ml Normal Saline (NS) IV Bag
 
 
 
 
 If NO > Preparation is required prior to proceeding.
 
 If YES > Proceed to Step 7 of this SOP

7.	
Clinic Staff obtains vitals.
 
 
• Vitals: 
 
✓ Blood Pressure;
 
✓ Pulse;
 
✓ Heart Rate;
 
✓ Respiratory Levels;
 
✓ SaO Levels;
 
✓ EKG (If required, per Practitioner's judgement); and
 
✓ PFT (May be obtained within the 3 days of scheduled treatment)
 
 
 
 
➤ If NO > Obtaining Patient vitals is required prior to proceeding.
 
➤ If YES > Proceed to Step 8 of this SOP

8.	
Clinician draws blood and affixes IV line to catheter.
 
 
• IV site is prepped and disinfected;
 
• Affix tourniquet to upper arm;
 
• Insert IV catheter into desired site;
 
• Remove needle from catheter;
 
• Affix Harvest PRP kit 30ml syringe to catheter and draw approximately 30ml of blood;
 
• Remove syringe and affix IV drip line to catheter;
 
• Check the patency and flow to make sure it is correct;
 
• Once correct, close off IV drip line until reinfusion; and
 
• Dispose of supplies in designated biohazard/sharps containers.
 
 
➤ If NO > Step must be completed prior to proceeding.
 
➤ If YES > Proceed to Step 9 of this SOP

10Mar2016 - version 2.0

LI-001

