18.	
Clinic Staff gives Patient post-op instructions.
 
 
• Has Clinic Staff advised the Patient of the below post-op care instructions and ensured that they understand said instructions; answering any questions or concerns? 
 
✓ Practitioner made available to Patient for additional education and questions;
 
✓ Advised of no submerging of incision site in pools, hot tubs, bath, etc. for 7 days post-op;
 
✓ Advised to avoid excessive lifting and bending for the next seven days; and
 
✓ Advised to use ice as needed for 15 minutes per session for pain or swelling.
 
 
 
 
➤ If NO > Step must be completed prior to proceeding.
 
➤ If YES > Proceed to Step 19 of this SOP

19.	
Clinic Staff to review all discharge paperwork provided and answer any questions pertaining to treatment and discharge.
 
 
• Has Clinic Staff advised the Patient of the below post-care instructions and ensured that they understand said instructions; answering any questions or concerns? 
 
✓ Briefly review and explain the discharge folder contents to Patient;
 
✓ Review LI follow-up procedures; and
 
✓ Review Patient Journals for quality of life outcome data.
 
 
 
 
➤ If NO > Step must be completed prior to proceeding.
 
➤ If YES > Proceed to Step 20 of this SOP

20.	
Has Clinic Staff updated EMR as required?
 
 
• Capture procedure as required in the EMR: 
 
✓ Vitals
 
✓ Testing Conducted
 
✓ Medications Administered
 
✓ Lot Numbers and expirations (As Applicable);
 
✓ Dosage(s)
 
✓ Site(s) of Procedure and/or Administrations (Left vs Right, and location)
 
✓ Route (PO, SubQ, IM, IV, Etc.); and
 
✓ Any additional notation required.
 
 
 
 
➤ If NO > Step must be completed prior to moving forward.  ➤ If YES > Proceed to Step 21 of this SOP

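### Once an infusion starts, the three supplied infusion SOPs list no vital-sign measurement and no symptom question, so mild or transient events that patients do not volunteer can go unrecorded

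*Combined protocol and SAP*

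**What the plan says.** Three of the supplied SOPs include an infusion: Venous, Bone Marrow Aspirate, and the venous branch of Discharge Treatment Day. Each has one vitals step for the infusion day:

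- Venous Step 11: "Has Clinic Staff obtained the following vitals"
- Bone Marrow Step 9: "Has the Clinic Staff obtained Patient Vitals"
- Discharge Step 7: "Clinic Staff obtains vitals"

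The lists cover blood pressure, pulse, heart rate, respiration and oxygen saturation, plus EKG and PFT. None includes temperature.

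Once the infusion is running, each SOP has an oversight step (Venous 21, Bone Marrow 40, Discharge 13), worded "Clinic Staff conducts on-going oversight of Patient during administration". The single item under it is "Has Clinic Staff confirmed the patency and flow are correct".

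After the infusion, the steps respond to what the patient raises:

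- Venous Step 24: "Has Clinic Staff provides Patient with discharge folder and post-care instructions and answered any Patient questions or concerns"
- Bone Marrow Step 42: "ensured that they understand said instructions; answering any questions or concerns"
- Discharge Step 19: "Clinic Staff to review all discharge paperwork provided and answer any questions pertaining to treatment and discharge"

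Discharge Step 14 also has the practitioner made available to the patient. Section 11 plans adverse-event follow-up at 2 weeks, 3 months and 6 months and makes the calls voluntary. CL-005 section H allows two attempts for the 2-week call.

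**The concern.** Research question 1 asks whether collecting and giving the cells is safe. Section 6 makes measuring adverse events part of the quantitative arm. Hypothesis 5b is framed in terms of events reported, and expects none. When a safety result is a count of reported events, how events are looked for is part of the measurement.

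Section 13 names risks that can be brief or mild: a reaction to the cells, fever, numbness or tingling, and breathing difficulty that is usually temporary. With the SOPs followed as written, recording such an event on the treatment day depends on staff noticing it or the patient mentioning it. A drop in saturation or blood pressure that has resolved by the next contact leaves no listed trace. Fever has no listed measurement at all, before or after. The resulting error runs in one direction, towards fewer recorded events.

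**Working it through.** This is a check of step order; the plan gives no figure to reproduce. The SOPs say their steps run in sequence unless a skip is instructed, so a step's number fixes its timing relative to the infusion.

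| Pathway | Vitals | Infusion starts | Oversight item | Line removed | Vitals after start | Symptom question after start |
|---|---|---|---|---|---|---|
| Venous | Step 11 | Step 20 | Step 21: line only | Step 23 | none listed | none listed |
| Bone Marrow | Step 9 | Step 39 | Step 40: line only | Step 41 | none listed | none listed |
| Discharge, venous | Step 7 | Step 11 | Step 13: line only | Step 14 | none listed | none listed |

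**Count.** After the infusion starts, 0 of 3 pathways list a vitals measurement and 0 of 3 list an active symptom question.

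**Before the infusion.** Symptom-directed steps do exist: chief complaint, history and physical exam at Venous 12, 14 and 18 and Bone Marrow 10, 12 and 15, and a comfort check at Bone Marrow 21. All precede the infusion. The venous discharge branch lists no chief-complaint step. Its Step 9 tells the practitioner the patient can be seen, without fixing when.

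**Other steps after the infusion starts.** These are the nebulizer (Venous 22, Discharge 12), line removal, dressing, instructions, questions, paperwork, EMR entry and, on discharge day, a Satisfaction Survey. The EMR lists (Venous 25, Bone Marrow 43, Discharge 20) record vitals but call for no new set, and they name no adverse-event item.

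**Next planned contact after each kind of infusion.**

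- Venous, not the last day: the next treatment day, with vitals taken before that day's infusion.
- Bone marrow: the next-day visit, with vitals and a site check (Discharge 15 and 16).
- Venous, discharge day: the voluntary call at 2 weeks, that is, 14 days.

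**Direction.** Let N be the true number of treatment-day events, m the share that are mild or transient and not volunteered, and p the chance that such an event is recorded anyway. If all other events are recorded (assumption), then recorded events = N × [1 − m(1 − p)]. This is below N whenever m > 0 and p < 1. The documents give neither m nor p, so the sign is known and the size is not.

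**The case against.** The strongest reply is that a short checklist is not the whole of care. The oversight step concerns the patient, not just the line, and staff may observe more than is written. Section 11e says staff are trained to identify and report adverse events. CL-005 section F puts an emergency-certified provider on site. Questions are answered after the infusion, and the practitioner is made available at Discharge 14. Patients keep a journal from discharge to help recall, and adverse events are sought at 2 weeks, 3 months and 6 months.

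Some relevant material also could not be seen: incident policy OP-004, any flowsheets, the content of the Satisfaction Survey, and Office Manager Steps 10 and 11. Any of these might already schedule the checks.

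Much of this stands. It means overt and volunteered events should be caught, and that the finding is limited to the three infusion SOPs. It does not close the gap. Training and reporting rules act once an event is noticed, and answering questions relies on the patient to raise it. The journal is for quality of life and starts after the infusion. No supplied page measures a vital sign or asks about symptoms after infusion start on the same day.

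A reader might infer that patients are unmonitored during infusion or that adverse events are not collected. The safeguards above contradict both readings. A reader might also infer that all 200 anticipated patients are affected, giving at least 200 infusions. That does not follow. Section 11 still lists an adipose procedure, although the CL-005 revision history removes adipose language, so some patients may fall outside these SOPs.

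**Conclusion.** The point holds in a limited form. Under the three supplied infusion SOPs, same-day detection after infusion start is passive, so transient or mild events that are not volunteered can go unrecorded. The gap is clearest after the venous discharge-day infusion.

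The effect is a lower event count and rate for research question 1, moving towards 5b. The documents do not support saying that 5b is bound to be confirmed: a single recorded event already contradicts it. The size of under-recording and the number of infusions affected cannot be estimated. The plan does not give the procedure mix, the number of treatment days, or which vital-sign changes count as adverse events.

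The conclusion assumes the SOPs are followed as written and that no document outside those supplied schedules the checks. It is worth fixing because the fix is cheap and helps both patient safety and the reported result. Confidence is medium.

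**What to change.** 1. Before release (Venous 23, Bone Marrow 41, Discharge 14), add one repeat set of vitals with temperature and one short symptom question. Add temperature to the baseline lists (Venous 11, Bone Marrow 9, Discharge 7).
2. Add two fields to the EMR lists (Venous 25, Bone Marrow 43, Discharge 20): adverse event yes/no, and onset time.
3. In section 12b, report treatment-day adverse events per infusion, by SOP, and state that zero reported events is not read as zero events.

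A set of vitals during the infusion, and a call 1 to 3 days after the venous discharge-day infusion, are optional; the documents do not settle whether they are needed. If OP-004, a flowsheet or another document already schedules these checks, cite it in the steps above instead.

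**Cost.** A few minutes of existing staff time per infusion. At an assumed 3 to 5 minutes per set, 100 infusions take 100 × 3 = 300 to 100 × 5 = 500 minutes, or 5 to 8.3 hours. Add two EMR fields, edits to three SOPs and section 12b, and IRB approval before use. If the call is added, section 11 and CL-005 section H also change.

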## 1. INTRODUCTION

The purpose of the Lung Institute is to collect and process a patient's own stem cells and platelet rich plasma (PRP) and deliver them back to the patient same-day through an intravenous catheter and sometimes by nebulizer. Lung Institute's treatment is limited to self-funded patients with chronic lung diseases – chronic obstructive pulmonary disease (COPD) and interstitial lung disease (ILD). The patient's stem cells and platelet rich plasma are collected through venous, adipose or bone marrow harvesting techniques. After the stem cells and platelet rich plasma have been isolated they are administered back to the patient. An inhaled antioxidant, glutathione, is administered during treatment to help mobilize lung secretions.

Researchers have demonstrated that using autologous stem cells (those derived from the patient) with minimal manipulation is safe and effective to promote the healing of lung tissue affected by COPD and ILD. The administration of glutathione to mobilize secretions in the lung has been determined a safe and effective addition to treatment (Jones, 2011).

In a pilot study conducted by [name] at Lung Institute Nashville, after following approximately 100 treated patients, [name] discovered that within three months of treatment, 84 percent of patients reported improvement in their quality of life (Coleman, 2016). For millions of people suffering from COPD, a natural decline in pulmonary health is a harsh reality. Based on these results, stem cell therapy gives promise to improving their quality of life and slowing down the progression of disease.

At this time, autologous stem cell collection and administration is not commercially available and therefore is considered an investigational agent under the standards of the Texas Medical Board.

Lung Institute's collection and administration of stem cells as investigational agents in the state of Texas is part of a systematic program monitored under the strict oversight of Lung Institute's business associate and medical management services company, Regenerative Medical Solutions (RMS). Lung Institute and RMS are committed to the highest level of concern and caution for the welfare, safety and comfort of the patient to whom the cell therapy treatment is administered.

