### 13. RISK AND BENEFIT ANALYSIS

All measures are taken to minimize or mitigate risks to the patient. The following lists the potential risks as indicated on the patient informed consent:

- **Adverse reaction to stem cells** - There is a possibility of an adverse reaction to the application of stem cells. This risk is minimized by using autologous (your own) unaltered stem cells.
- **Anemia** - There have been reports of anemia with harvesting of stem cells from the circulation. This risk is low. To minimize this risk we request blood work (CBC).
- **Embolus development** - An embolus is a clot that may be from blood or cells such as fat or bone marrow. There is a chance that an embolus or emboli (plural) may develop with stem cell procedures. This risk is low and is minimized due to our stem cells processing protocols.
- **Failure of the procedure** - There is a chance that undergoing stem cell application will not alleviate symptoms, resolve inflammation, or assist in regenerating tissue.
- **Fever** - Fever associated with stem cell harvesting usually responds to acetaminophen. If fevers persist, a work-up for infection must be completed.
- **Infection** - Infection may occur at the donor site where the bone marrow or fat was harvested or at the IV site and recipient site of application. To minimize risk infection prevention protocols are maintained and followed during the treatment process and patient education is provided on post treatment cleaning and wound care.
- **Pain** - Any procedure can result in pain. To minimize this risk we ask that our patients communicate any discomfort so that we can reduce or mitigate.
- **Numbness/tingling** – Although a low risk, this has been reported with leukapheresis (the process of separating stem cells from peripheral blood in the vein). Laboratory analysis may be required along with calcium infusion.
- **Respiratory difficulties** - Breathing difficulties (which are usually temporary) or post-operative pneumonia, may occur as a result of any procedure or surgery. Pulmonary embolus, a blood clot causing blockage of an artery in the lungs may occur as a result of any procedure or surgery. Pulmonary embolus may be fatal.
- **Stroke** - Though a low risk and unlikely, there is a possibility that a stroke will occur during the procedure or in the recovery period.

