- **Transfers of undiagnosed cancer** – There is a risk that undiagnosed cancer in the area where the stem cells are harvested may be transferred to the recipients area of transplantation. To minimize risks, stem cells will not be altered in any way, thereby reducing the risk of tumor induction by carcinogens.

Rev\_2/5/16 Page 8 of 10

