33.	
Practitioner takes harvested bone marrow aspirate to Lab area for processing.
 
 
• Has Practitioner made sure that processing area is clean and free from other samples, clutter, and any other risk of contamination?
 
 
➤ If NO > Step must be completed prior to proceeding.
 
➤ If YES > Proceed to Step 34 of this SOP

34.	
Practitioner transfers bone marrow aspirate to Harvest processing cup for centrifuge.
 
 
• Has practitioner placed bone marrow aspirate from 60ml syringe into blood chamber (red port) of process disposable (PD)?
 
 
➤ If NO > Step must be completed prior to proceeding.
 
➤ If YES > Proceed to Step 35 of this SOP

35.	
Practitioner inserts PD cup into centrifuge.
 
 
• Has Practitioner completed the following? 
 
✓ Practitioner places PD into Harvest centrifuge; and
 
✓ Presses "BMAC" button for processing
 
 
 
 
➤ If NO > Step must be completed prior to proceeding.
 
➤ If YES > Proceed to Step 36 of this SOP

36.	
Has Practitioner removed bone marrow concentrate from centrifuge?
 
 
• Practitioner withdraws excess plasma from white port of PD cup with syringe containing yellow spacers; 
 
✓ Draws off excess plasma until bubbles appear in syringe;
 
✓ Properly discard excess plasma syringe; and
 
✓ Use 20ml syringe to draw remaining PRP from the side compartment of PD cup, identified by the white port.
 
✓ Use PRP to wash walls of PD Cup at least twice; and
 
✓ Extract into a 20ml syringe.
 
 
 
 
➤ If NO > Step must be completed prior to proceeding.
 
➤ If YES > Proceed to Step 37 of this SOP

LI-001

37.	
Practitioner utilizes light system.
 
 
• Has Practitioner completed the following? 
 
✓ Place 20ml syringe of bone marrow aspirate final product in Adi-Light for 20 min.
 
 
 
 
➤ If NO > Step must be completed prior to proceeding.
 
➤ If YES > Proceed to Step 38 of this SOP

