38.	
Clinic Staff prepares final product for administration via IV bag.
 
 
• Has Practitioner completed the following? 
 
✓ Remove 20ml syringe of bone marrow final product from Adi-Light;
 
✓ Inject bone marrow final product into 100ml normal saline IV bag; and
 
✓ Inject 20ml PRP syringe from top of clean box into same 100ml normal saline IV bag.
 
 
 
 
➤ If NO > Step must be completed prior to proceeding.
 
➤ If YES > Proceed to Step 39 of this SOP

39.	
Clinic Staff administers final product via IV.
 
 
• Has Clinic Staff completed the following? 
 
✓ Clean Hep-Lock site with alcohol prep pad;
 
✓ Affix IV tubing of final product contents to Hep-Lock catheter;
 
✓ Open IV line (checking for proper flow and drip rate).
 
 
 
 
➤ If NO > Step must be completed prior to proceeding.
 
➤ If YES > Proceed to Step 40 of this SOP

40.	
Clinic Staff conducts on-going oversight of Patient during administration.
 
 
• Has Clinic Staff confirmed the patency and flow are correct?
 
 
➤ If NO > Step must be completed prior to proceeding.
 
➤ If YES > Proceed to Step 41 of this SOP

41.	
Clinic Staff discontinues IV line.
 
 
• Has Clinic Staff completed the following? 
 
✓ When final product has emptied IV bag, use NS (normal saline) flush to flush entire contents of IV line;
 
✓ Remove IV catheter;
 
✓ Place 2x2 gauze pad over site, affix coban bandage
 
✓ Instruct Patient to remove gauze and coban after 20 to 30mins; and
 
✓ Dispose of supplies in designated biohazard containers.
 
 
 
 
➤ If NO > Step must be completed prior to proceeding.
 
➤ If YES > Proceed to Step 42 of this SOP

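### Section 13 assures bone marrow patients that their cells are unaltered, but the documents never explain the compulsory 20-minute light step or say what it does to the cells

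*Combined protocol and SAP*

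**What the plan says.** **The procedure.** Section 11 of the protocol attaches an SOP for each cell therapy, and the bone marrow SOP is in the package. Its Step 37 is titled "Practitioner utilizes light system" and asks whether the practitioner has done the following: "Place 20ml syringe of bone marrow aspirate final product in Adi-Light for 20 min". A negative answer blocks the next step until this has been done. Step 38 begins "Remove 20ml syringe of bone marrow final product from Adi-Light" and then injects that product into the saline bag that is infused.

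**The risk statements.** Section 13 introduces its list as the risks given in the patient's informed consent. For adverse reaction to stem cells it says: "This risk is minimized by using autologous (your own) unaltered stem cells". For transfer of undiagnosed cancer it says: "To minimize risks, stem cells will not be altered in any way, thereby reducing the risk of tumor induction by carcinogens".

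**What is not said.** Section 13 does not mention light exposure. Apart from the name, the words in the step title and the 20 minutes, the device is not described: there is no purpose, wavelength, intensity or effect on cells.

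**The concern.** Two safety assurances, one of them about cancer, rest on a property of the cells that the documents do not establish for one of the treatment routes. The statement on tumour induction is absolute, because it rules out alteration of any kind. A compulsory, timed exposure of the product just before infusion is the sort of step such a statement ought to account for, and it does not.

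At stake is the accuracy of what bone marrow patients are told about risk. Section 14 treats informed consent as a priority, and section 13 says that its list mirrors the consent. If the basis for the reassurance is missing, those patients weigh two risks with more comfort than the documents justify.

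**Working it through.** The only number involved is the 20-minute duration, and there is no stated statistical figure to reproduce. The check is a comparison of passages.

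**1. Is the step compulsory, and does it act on what is infused?** Yes to both. Step 36 draws the marrow product into a 20 ml syringe, Step 37 places that syringe in the device and blocks progress until this is done, and Step 38 moves the same syringe's contents into the infusion bag.

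**2. Is it just a holding place while other work finishes?** The SOP does not read that way. In Step 16 the separate PRP syringe is set aside on the clean box until re-infusion. Only the marrow syringe goes into the device, for a fixed time, under its own numbered step. This suggests a purpose, but the SOP does not state one.

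**3. Which component is exposed?** Step 38 combines two syringes in one bag: the marrow product from the device and the PRP from the clean box. No light step is listed for the PRP. The infusion is a mixture, and only its marrow component is listed as exposed.

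**4. Which patients are affected?** The bone marrow route only. The Venous SOP and the venous branch of the Discharge SOP go from extraction to infusion with no light step.

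**5. How many risk items depend on non-alteration?** Section 13 lists 13 risks: adverse reaction, anemia, embolus, failure, fever, infection, pain, numbness, respiratory difficulties, stroke, transfer of cancer, incorrect cells and unintended differentiation. Two of the 13 (adverse reaction and transfer of cancer) cite non-alteration as the mitigation.

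**6. Do the documents support the two statements for bone marrow product?** Set side by side:

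| Section 13 | Bone marrow SOP |
|---|---|
| Adverse reaction: cells are unaltered | Step 37: 20 minutes in a light system, effect not stated |
| Tumour induction: "stem cells will not be altered in any way, thereby reducing the risk of tumor induction by carcinogens" | Step 38: the exposed marrow product is infused |

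To show a contradiction, the documents would have to say that the exposure changes the cells. They do not. To support the assurance, they would have to say that it leaves the cells unchanged, and they do not say that either. The statements are unsupported for this route, but they are not disproved.

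**The case against.** The strongest reply is that unaltered does not mean unprocessed in this protocol. Section 13 itself relies on processing as a safeguard against embolus: "This risk is low and is minimized due to our stem cells processing protocols". The bone marrow SOP adds anticoagulant, washes instruments with heparin, filters and centrifuges, and nobody would say that section 13 hides this. The Introduction speaks only of what researchers have shown about "using autologous stem cells (those derived from the patient) with minimal manipulation is safe and effective", which makes no promise about this particular product. One more handling step is therefore not automatically a contradiction.

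That stands, and it limits the point. A reader might infer that the procedure breaks the promise in section 13, or that the cells are altered. The documents do not support this, because no passage says what the device does, and any view on it would come from outside sources. The reply does not rescue the absolute wording, however. Accepting processing in general neither discloses the light exposure nor shows that it leaves the cells unaltered.

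A second reply is that the step is already part of the study, since section 11 attaches the SOP. This is correct, and section 11 does not spell out centrifuging or filtration either. The gap that matters is in the risk statements, not in section 11.

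A third is that the consent form is not available for this review and may explain the step. That cannot be checked. What can be said about the consent rests on section 13's own statement that its risks are taken from it.

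**Conclusion.** The point holds as one about risk disclosure. For bone marrow patients, two absolute assurances in section 13 have no stated basis, given a compulsory light exposure whose purpose and effect are not described and which section 13 does not mention.

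**Size.** Every patient treated by the bone marrow route is affected. Section 12a anticipates 200 patients without splitting them by procedure, so the number cannot be narrowed.

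**Limits.** A reader might also infer that the trial's results would be mislabelled as results of unaltered cells. The documents do not support that. The aims, research questions, hypotheses and design refer to autologous treatment and never to unaltered cells, and section 12b plans only descriptive FEV1 summaries. No endpoint, estimate or analysis depends on the word. Nor would it be accurate to call the whole infusion light-exposed, because it also contains PRP for which no such step is listed.

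**Weight.** This should be corrected, but it ranks below a must-fix. Confidence is high in the textual facts only. Whether the exposure alters the cells is left open. The conclusion assumes that the consent's risk list matches section 13, as section 13 says.

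**What to change.** The sponsor and Medical Director should reconcile the two risk items in section 13 with Steps 37 and 38 of the bone marrow SOP.

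- State the device's purpose and what is known of its effect on the cells.
- If it can be documented that the exposure leaves the cells unaltered, cite that as the basis for the two statements.
- Otherwise, remove or qualify both statements for bone marrow patients, in section 13 and in the matching consent risks. Disclose in the same places that the marrow component undergoes a 20-minute light exposure before infusion, and that no such step is listed for the PRP component.

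Whether the step itself should be kept is for the sponsor and Medical Director, and this review takes no position on it.

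The cost is revised wording in the protocol and consent, one IRB amendment, and a less reassuring risk statement. No change to sample size, endpoints or analysis is needed.
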